Actual schedule of diabetes clinic visits for a given patient deviates substantially from the typical quarterly appointments.	Adolescents will not be followed for more than 12 months. If a clinic visit occurs between 9 and 12 months after the Baseline Visit, the measures designated for collection at Visit 5 will be collected at that visit, regardless of the number of previously completed study visits for that adolescent.
Indecision between adolescent and parent resulting in a period in which no clear decision is made.	Measurement plan will have slightly different measurement schedules for families who clearly decide to accept CSII or CGM, for families who clearly decide to decline CSII or CGM, and for families who either cannot reach a decision or wish to defer decision making until a later date.
Adolescent is considered to be a candidate for both CSII and CGM simultaneously.	Adolescent will be given access to both the CSII and CGM decision aids.
Adolescent already on CSII is a candidate for the so-called "low glucose-suspend" insulin pump.	Adolescent will be given access to both the CSII and CGM decision aids and especially encouraged to review the content related to the closed-loop artificial pancreas.
Adolescent and/or parent want to consider CSII or CGM, but HCP disagrees.	Adolescent is considered ineligible for the study until HCP supports the adolescent's candidacy for CSII or CGM.
Enrolled family does not have a computer for CGM or CSII downloads or for online completion of study questionnaires.	Downloads of devices and completion of questionnaires will be done in the clinic.

Adolescent initiates either CSII or CGM and then later decides to consider adding the other device to the diabetes regimen.	Device downloads will be collected for each device from the time the device is received and initialized. Measures of decision quality and device knowledge will be completed at the next study visit after receipt and initialization of the second device.
-----------------------------------------------------------------------------------------------------------------------------	-------------------------------------------------------------------------------------------------------------------------------------------------------------------------------------------------------------------------------------------------------------

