Each parent/adolescent dyad will receive a \$25 gift card to a discount retail chain after completing the measurement protocol at Visits 1, 3 and 5, which are the most burdensome of the visits. At each study visit in which an adolescent brings either an insulin pump or CGM to the visit for downloading, the adolescent will receive a \$5 gift card for each such device that is downloaded.

Measures obtained at Baseline only

Demographic characteristics will be measured at study entry using a General Information Form as in our previous studies. This measure ascertains the child's age, diabetes duration, gender, race/ethnicity, and relevant medical history (including past CSII or CGM use) and the parents' income, educational level, occupational category, family structure, race/ethnicity, gender and age. The Hollingshead Four Factor Index of Social Status¹⁵⁹ will be calculated to quantify household socioeconomic status. Participants will be asked to indicate their preferred mode of contact from study staff (e.g. text, phone, e-mail, specific social media). Administration time is about 15 minutes.

Rapid Estimate of Adult/Adolescent Literacy in Medicine This brief test of health literacy will be administered in person to parents and adolescents by the research coordinator at baseline.¹⁶⁰

Diabetes Numeracy Test This 14-item test of numeracy skills pertinent to T1D care will be administered in person to parents and adolescents by the research coordinator at baseline.¹⁶¹

Measures obtained at all 5 quarterly clinic visits

Glycated hemoglobin: Finger-Stick blood samples will be obtained at each quarterly visit and glycated hemoglobin (HbA_{1C}) will be determined using the point of care device currently used at each clinic (typically a DCA2000 or DCA2000plus). These devices have been found to yield results that are highly correlated with benchmark central laboratory assays and that are considered to be acceptable outcomes measures in diabetes clinical trials. HbA_{1C} reflects average glycemia over the prior 2-3 months and is considered a secondary outcome measure in this study.

Hypoglycemia Diary: Parents will record each episode of moderately severe (symptomatic and requiring

assistance from others) or severe hypoglycemia (with seizure or loss of consciousness) using a diary form developed for this purpose in [name] ongoing CGM trial. Frequency of moderately severe and severe hypoglycemia is considered a secondary outcome measure in this study.

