Insulin Pump Use Profile/CGM Use Profile (P,C)					
Hypoglycemia Diary (B)					

HbA _{1c} (A)					
Rapid Estimate of Adult/Adolescent Literacy in Med. (B)					
Diabetes Numeracy Test (B)					
Diabetes Self Management Profile-Self Report (B)					
Test of CSII or CGM Knowledge (B)					
Decision Regret Scale (B)					
SURE Test (B)					
Diabetes Technology Questionnaire (B)					
SMDM Satisfaction Scale (B, HCP)					
Description of Decision Making Process (B)					
Decision Aid Utilization Statistics (Monthly Reports)					

*Baseline assessment (0 Months) will occur just prior to randomization to SMDM or UCP. Respondents for each measure are HCP =Adolescent's diabetes health care provider; P = Parent; A= Adolescent; B = Both. All measures are obtained from both the SMDM and UCP groups unless otherwise stated. The Decision Regret Scale, SURE Test and the Description of the Decision Making Process may be repeated at other visits if additional medical decisions (CSII, CGM) are raised for consideration. The Test of CSII or CGM Knowledge will be administered at the first post-decision visit, which is expected to be Visit 2 for most participants. As mentioned above, those who enroll after 3/31/15 are likely to be followed for only 6 months unless PCORI

decides to allow no-cost extensions.

B.5. Statistical Analyses:

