Demographic and baseline characteristics (age, race, ethnicity, family composition, marital status, SES), primary and secondary end points, and biochemical, psychological, and behavioral variables will be summarized by intervention groups. One way analysis of variance (ANOVA) of each continuous baseline characteristic and a Fisher exact test/chi-square test/CMH test for each categorical variable will be used to compare the intervention groups at baseline. These comparisons will be used to evaluate the balance of demographic and baseline characteristics among intervention groups. Analyses of primary and secondary end points will be adjusted for significantly imbalanced baseline characteristics. For those measures completed separately by parents and youths, when parent and youth scores are correlated at $r > .70$, a combined parent-adolescent score for that variable will enter analyses. Otherwise, separate analyses will be completed on parent and adolescent scores. A mixed models (or multilevel modeling) approach will be used to test the hypotheses listed below.¹⁶⁹⁻¹⁷² The methods advocated by Holmbeck¹⁷³ will be used to evaluate baseline variables that moderate/predict SMDM-UCP treatment effects on primary study outcomes. Candidate moderator variables will include SES, youth age and gender, race/ethnicity, family structure, and health literacy and numeracy. The methods advocated by Holmbeck¹⁷³ will also be used to evaluate variables that may mediate SMDM-UCP treatment effects on primary study outcomes. In each case, these will include measures that are obtained serially and concurrently with the primary study endpoints. SAS subroutines for addressing the potential confounding influences of time- dependent covariates (e.g. youth age) will be employed as needed in these mediational analyses. With five measurement points for HbA_{1c} and hypoglycemia, the proposed mixed models approach will be capable of detecting longitudinal associations among study variables that are non-linear in form.

Hypothesis 1: Compared to UCP, the SMDM group will have significantly more favorable status in terms of indices of optimal use of CSII or CGM, scores on the CSII or CGM Knowledge Test, SURE Test, Decision Regret Scale, Diabetes Technology Questionnaire and SMDM Satisfaction Scale at each follow-up measurement point.

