Hypothesis 2: Compared to UCP, the SMDM group will have significantly more favorable status in terms of scores for treatment adherence (DSMP-SR), HbA_{1c}, and frequency of moderately severe or severe hypoglycemia at each follow-up measurement point.

Hypothesis 3: Effects of SMDM on indices of optimal use of, and satisfaction with, CSII or CGM will be mediated by changes in the measures of decision quality (Test of CSII or CGM Knowledge, Decision RegretScale, SURE Test, Decision Satisfaction Scale).

Hypothesis 4: Significant moderators of benefit from SMDM along the measured outcomes will include baseline measures of socioeconomic status, health literacy and numeracy, youth age, and family structure.

Hypothesis 5: SMDM will have indistinguishable beneficial effects on the primary study outcomes regardless of which clinical decision (CSII or CGM) was the focus of the SMDM intervention.

Statistical Power Statistical power to detect treatment effects of interest on the primary endpoints was assessed using the online DSS Research Statistical Power Calculator.¹⁷⁴ With enrollment of 166 eligible youth and parents and attrition of 10% over the 12-month study, and a resulting “Completer” sample size of 150, the study will have statistical power of .87 to detect a moderate treatment effect of ~0.4 SD on the measures of decision quality and CSII or CGM optimal use. Even though statistical power remains adequate for detection of somewhat smaller treatment effects, effects of less magnitude are unlikely to have sufficient clinical significance to warrant the added cost and inconvenience of implementing SMDM.

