Inclusion Criteria for Parents: Primary diabetes caregiver of index child; Anticipates continued medical care for T1D at Nemours for subsequent year; Capable of participating in conversations during medical visits; Routinely accompanies adolescent to diabetes clinic visits.

Exclusion Criteria for Parents: Inability to read/comprehend study questionnaires and decision aids in English; Open abuse/neglect case with any child protection agency over the prior 3 years; Evidence of frequent changes in the adolescent's household or living arrangements.

Sources of Research Material

Sources of research material include downloaded data from glucose meters, insulin pumps and continuous glucose monitors (primary outcome measures), questionnaires completed by youth and parents each 6 months regarding quality of life, burden of disease management, diabetes self-efficacy, decision quality, decisional conflict, health literacy, and treatment adherence, glycated hemoglobin tests performed at a central laboratory, glycated hemoglobin results obtained via point-of-care testing (DCA-2000+) at each clinic visit, and quarterly collection of hypoglycemia diaries for recording of symptomatic hypoglycemic episodes.

Methods of Recruitment

Participants will be recruited from among eligible patients treated for type 1 diabetes mellitus at any Nemours Children's Clinic location or at the Barbara Davis Center. Endocrinologists will be asked to identify patients from their clinics who are good candidates for participation in this research. Prospective participants will then be given a letter signed by [name] and the attending endocrinologist, either in clinic or by mail. This initial contact will be followed with a telephone call to the parents to determine eligibility and interest in study participation. Parents/caregivers and youth will sign IRB-approved consent/assent documents.

Assessment of Research-Related Risks

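### The hypoglycemia diary endpoint has two conflicting respondents, a Visit 1 value that can only be recall, and no allowance for the time each count covers

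*Combined protocol and SAP*

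**What the plan says.** - **B.3 Measures** places the diary among the measures taken at all five quarterly visits: "Hypoglycemia Diary: Parents will record each episode of moderately severe (symptomatic and requiring" another person's help, "or severe hypoglycemia (with seizure or loss of consciousness) using a diary form developed for this purpose". The frequency of these two grades is a secondary outcome.
- **B.4 Measurement Schedule** has a row that begins "Hypoglycemia Diary (B", with the legend "P = Parent; A= Adolescent; B = Both". The row is ticked from Visit 1 (month 0) to Visit 5. The footnote puts baseline just ahead of randomization.
- **B.5 Statistical Analyses** lists the diary under secondary efficacy. Hypothesis 2 predicts a better result in the shared decision-making (SMDM) arm on "frequency of moderately severe or severe hypoglycemia at each follow-up measurement point". B.5 also says "With five measurement points for HbA_{1c} and hypoglycemia, the proposed mixed models approach will be capable" of finding non-linear associations. Parent and youth scores are merged if they correlate above .70 and are otherwise analyzed apart.
- **B.2, Practical considerations**, anticipates this: "Actual schedule of diabetes clinic visits for a given patient deviates substantially from the typical quarterly appointments". Visit 5 measures are then taken at any clinic visit 9 to 12 months after baseline, however many visits came before.
- **B.1** gives 12 or 6 months of follow-up by enrollment date. Recruitment Plan C frees remote families' study visits from clinic visits. B.3 relies on mixed models to absorb irregular schedules.
- **C.3** allows no research procedure before signed consent and assent. Its list of data sources mentions "quarterly collection of hypoglycemia diaries for recording of symptomatic hypoglycemic episodes".

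**The concern.** An event-count endpoint needs four things settled: who reports, what counts as one event, when observation starts, and how long it lasts. Here the respondent is contradictory, the start is undefined at Visit 1, and the duration is missing.

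The last gap matters most, because the plan appears to have an answer and does not. A mixed model with visit time as a covariate places each value on the time axis. It does not know that one diary covers three months and another six. The other remedies in B.5, transformation or a non-parametric method, do not supply that information either.

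At stake are the Hypothesis 2 contrast for hypoglycemia and any statement about its course over five points.

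**Working it through.** **Respondent.** B.3 (parents) and the B.4 code (both) cannot both hold. Under the code, the .70 rule in B.5 applies, but it was written for scale scores. The plan does not say how a composite is formed. Take one true episode:
- reported by both: average (1 + 1)/2 = 1; sum 1 + 1 = 2
- reported by one only: average (1 + 0)/2 = 0.5; sum 1 + 0 = 1

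Neither rule counts each episode exactly once in both cases. Matching entries by date does.

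**Visit 1.** Consent precedes data collection (C.3), and baseline just precedes randomization (B.4). No run-in is described in Recruitment Plans A to C. A quarter of prospective diary therefore cannot exist at month 0. Visits at 0, 3, 6, 9 and 12 months bound 5 − 1 = 4 intervals. A participant followed for 6 months contributes two.

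**Time covered.** Assume each diary runs from the previous collection; the documents do not say. Then:

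expected count = rate × months covered

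At a constant rate, a diary collected at month 12 covers about 3 months if the preceding quarterly visit was kept and 12 if no earlier visit was. The expected count then varies by a factor of up to 12/3 = 4. Totals over 12 and 6 months of follow-up differ by 12/6 = 2. B.5 defines its device endpoints per day but gives the diary no denominator.

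**Effect on the arm comparison.** The plan states no event rate, dispersion or power for hypoglycemia, so there is no figure of its own to reproduce. Its one power figure concerns decision quality and device use and has no bearing here. With no true effect, the expected count ratio is the ratio of mean gaps:
- 3 vs 3.5 months: 3.5/3 = 1.17 (reversed, 3/3.5 = 0.86)
- 3 vs 4 months: 4/3 = 1.33 (reversed, 3/4 = 0.75)

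A null simulation checked the test itself. From the plan: 75 per arm (150 completers, 1:1 allocation) and two-sided 0.05. Assumed: 0.5, 2 or 6 episodes per patient-year; gamma variation between patients with variance 1; individual gaps uniform within ±33% of the arm mean; one interval; 10,000 trials. Raw counts were compared by difference in means over its standard error. Rates were total events over total time, with a robust standard error.

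| Mean gap, months | Episodes per year | Count ratio | Type I, counts | Type I, rates |
|---|---|---|---|---|
| 3 vs 3 | 0.5 / 2 / 6 | 1.005 / 1.003 / 1.002 | 0.051 / 0.048 / 0.049 | 0.052 / 0.047 / 0.048 |
| 3 vs 3.5 | 0.5 / 2 / 6 | 1.169 / 1.163 / 1.162 | 0.065 / 0.085 / 0.107 | 0.053 / 0.050 / 0.053 |
| 3 vs 4 | 0.5 / 2 / 6 | 1.332 / 1.338 / 1.332 | 0.094 / 0.184 / 0.268 | 0.053 / 0.050 / 0.053 |

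The rate ratio lay between 0.996 and 1.004 in all nine settings. Uneven gaps shared by both arms left the test valid. Gaps that differed by arm did not, and dividing by time covered restored it.

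**The case against.** The strongest reply is that nothing here shows a biased comparison. Allocation is 1:1 within site, the same diary rules apply to both arms, and both arms' visits follow regular clinic appointments. This stands. A reader might infer that the Hypothesis 2 result will be wrong, but that needs a difference between arms in time covered or in reporting, and the documents show neither. The extra SMDM contacts make one plausible. However, B.2 also says the educator's summary is discussed at the next clinic visit, so an added clinic visit is not established.

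A reader might also infer that sites will count different events because C.3 mentions only symptomatic episodes. B.3 and Hypothesis 2 agree on the two grades, and the C.3 line is an inventory entry. It is loose wording, not a rival definition.

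Nor is the diary the trial's only acute-safety measure by the plan's own account. B.5 classes it as secondary efficacy, and C.3 provides for reports of unanticipated problems.

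Visit 1 lies outside the follow-up contrast in Hypothesis 2. That is right: a weak Visit 1 value harms baseline adjustment and the five-point trajectory, not the follow-up comparison itself.

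Finally, frequency could mean a rate, and the diary form, which sits in a separate appendix not available here, may state respondent, dates and look-back. That limits certainty about data capture. It would not remove the B.3/B.4 contradiction or put a denominator into the analysis section.

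**Conclusion.** The point holds as a specification fault in a secondary endpoint that should be corrected. Three parts rest on the text alone: the contradictory respondent with no count-once rule, a Visit 1 value that can only be recall but is counted as a fifth point, and an event frequency without person-time where unequal intervals are expected. The named remedy, mixed models, does not address the third.

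The numerical effect is conditional. With equal time covered it is noise and ambiguity (type I error 0.048 to 0.051). With mean gaps of 3 vs 3.5 months, the null count ratio is about 1.17 and type I error 0.065 to 0.107. With 3 vs 4 months, they are about 1.33 and 0.094 to 0.268. These gaps, the event rates and the dispersion are assumptions, and they presume that raw counts per visit would be analyzed.

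**What to change.** 1. Reconcile the respondent in B.3 and B.4. Require one dated entry per episode and, if both report, match by date so that each episode counts once. Exempt the diary from the .70 rule.
2. Align the C.3 wording with B.3 and Hypothesis 2.
3. Issue the diary at Visit 1 and collect it at Visits 2 to 5. Label any Visit 1 value as recall over a stated window, and use it only as a covariate.
4. Record the start and end date of each diary. Analyze episodes per patient-time over the four post-baseline intervals with an over-dispersed count mixed model and a log person-time offset. This stays within the plan's mixed-model approach.
5. In B.5, change five measurement points to four for hypoglycemia; HbA1c keeps five.

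The cost is protocol wording, two date fields on an existing form, one offset term, and the loss of one nominal time point that could not have been a prospective diary.
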